INTRODUCTION AND OBJECTIVES

1- Abstract

Several immune checkpoint inhibitors targeting the PD-1 pathway have been developed with clinical trials showing an approximately 20% durable response in unselected patients with advanced non-small cell lung cancer (NSCLC). At the moment, no clear biomarker exists to accurately predict anti-PD1/PDL1 tumor responsiveness. The goal of this study is to broadly discover and evaluate the utility of blood based biomarkers for use in measuring and predicting response to immunotherapy in patients with lung cancer.

2- Background

Despite significant advances in detection and therapy, lung cancer remains the number one cause of cancer related death in both men and women worldwide (1). Most patients are diagnosed at an advanced stage with poor overall survival. NSCLC is the most common histotype representing 85% of new diagnoses (2), and the overall five year survival rate of patients with NSCLC is 16% (3). Improved understanding of the interaction between tumors and host immune surveillance has enabled the development of several immune checkpoint inhibitors targeting the PD-1/PD-L1 pathway that have shown an approximate 20% durable response in unselected patients with advanced NSCLC, and improved response rates in select patients with PDL1 expression (Reck, NEJM 2016). Preliminary data suggest that detection of tumor PD-L1 protein expression on human cancers using chromogenic-based immunohistochemistry (IHC) in formalin-fixed paraffin embedded tissue samples (FFPE) may predict clinical response to PD-1/PD-L1 directed therapy (4,5). However, meaningful responses have also been observed in PD-L1 negative patients. Moreover, use of IHC may be limited by access to tissue as well as assay variability and interpretive subjectivity. In addition, conventional radiographic assessment of treatment response using WHO criteria (Response Evaluation Criteria in Solid Tumors [RECIST]) does not fully capture the response patterns of immunotherapeutic agents often necessitating frequent repeat imaging to assess a therapeutic response. Mutation burden and neoantigen expression have been evaluated as potential biomarkers for immunotherapy, however there is no validated biomarker to follow these changes yet. As a result, a biomarker that could accurately predict the patients most likely to derive benefit from immunotherapy, as well as monitor response to treatment would be of significant clinical utility.

One biomarker that is being increasingly utilized for the non-invasive monitoring of patients with various malignancies is cell-free DNA (cfDNA). cfDNA consists of short double-stranded DNA fragments shed into the blood by tumor cells undergoing apoptosis or necrosis. We and others have shown that cfDNA can be readily extracted and sequenced from NSCLC patient blood for mutation detection and disease monitoring (Thompson J et al. CCR 2016; Couraud S et al. CCR 2014; Oxnard GR et al. CCR 2014; Newman AM et al. Nature Medicine 2013). While surgically resected tumor or fine needle aspirate have traditionally been the source of tissue for molecular monitoring, these samples often provide insufficient and/or inferior quality DNA for sequencing, and can under-represent the full molecular heterogeneity of the patient's disease, especially in the setting of metastasis. cfDNA thus represents a non-invasive approach for patient monitoring and may allow for a "liquid biopsy" for genomic alterations of the primary or metastatic tumor, monitoring of the disease status, and/or development of resistance to therapy.

In this study, we will collect blood and urine specimens from patients receiving immunotherapy as part of their standard of care for the treatment of NSCLC. We will use various platforms for measurement of new biomarkers, and these biomarkers will be assessed for their ability to predict responsiveness

PROJECT TITLE: A PILOT STUDY TO DEVELOP PREDICTIVE BIOMARKERS FOR THE RESPONSE TO

IMMUNOTHERAPY IN LUNG CANCER

PRINCIPAL INVESTIGATOR/FACULTY SPONSOR: [name], MPH

PROTOCOL SUMMARY VERSION DATE: August, 2018 (VERSION 2)

to immunotherapy, correlation with radiographic response, ability to detect lung cancer specific genetic changes present in the primary tumor (e.g analysis of cfDNA for EGFR mutations), and impact on prognosis (response to therapy, progression free survival and overall survival).

Portions of the blood and urine samples drawn will also be stored for future research.

3- Study Objectives

The overall objective is to develop a comprehensive system to collect blood and urine samples from patients with NSCLC receiving immunotherapy

Primary Outcome Variable

1. Discovery and validation of new blood based biomarkers that predict response to immunotherapy in NSCLC

Secondary Outcome Variable

1. Storage of samples for future research endeavors

4- Location

Abrahamson Cancer Center at the Hospital of the University of Pennsylvania and Penn Presbyterian Medical Center

STUDY DESIGN

5- General Design

Single center, longitudinal cohort study of NSCLC patients receiving immunotherapy with biomarker evaluation.

This is an observational study. Biomarkers that are detected in CLIA certified laboratories and are already part of standard of care in the management of lung cancer patients (e.g. circulating tumor DNA) may be disclosed to the treating physician and care may be altered based on routine practice. Biomarkers that are in research development and/or not performed in CLIA certified laboratories will not be disclosed to treating physician and no treatment decisions will be based on these results.

The organizational structure will support the collection of peripheral blood and urine samples from subjects with NSCLC receiving immunotherapy for evaluation of circulating biomarkers. Physicians, nurse practitioners, and physician assistants will identify subjects with NSCLC who are scheduled to receive an immune checkpoint inhibitor as part of their routine clinical care at the University of Pennsylvania. The subjects will be consented for the collection of blood and urine samples. Given the exploratory nature of this study and that the hypotheses for circulating tumor material in NSCLC patients receiving immunotherapy will adapt as information from this analysis proceeds, the timeline and frequency of blood collection are not defined. The frequency of research blood collection will not exceed the lesser of 50 mL or 3 mL/kg in an 8 week period and will not occur more frequently than 2 times per week. Blood will generally be collected at the time of routine phlebotomy for the management of their disease, but in rare instances the

PROJECT TITLE: A PILOT STUDY TO DEVELOP PREDICTIVE BIOMARKERS FOR THE RESPONSE TO

IMMUNOTHERAPY IN LUNG CANCER

PRINCIPAL INVESTIGATOR/FACULTY SPONSOR: [name], MPH

PROTOCOL SUMMARY VERSION DATE: August, 2018 (VERSION 2)

subject may be asked to provide only a research blood sample if the timing of the routine phlebotomy does not correlate with the timing necessary for the study. Urine specimens will be obtained in a sterile specimen cup.

Duration

The total study duration will be 5 years. Subjects will be considered active participants on days of blood acquisition. Baseline data will be collected by chart review. Cancer outcome data may be collected longitudinally by chart review only until the end of the study.

SUBJECT SELECTION & WITHDRAWAL

6- Inclusion and Exclusion Criteria

A. Inclusion Criteria

1. Advanced Metastatic NSCLC
2. Scheduled to initiate an immune checkpoint inhibitor
3. Age ≥ 18 years
4. Able to provide informed consent

B. Exclusion Criteria

1. Other, unrelated, concomitant active, invasive malignancy

7- Vulnerable Populations

Although vulnerable populations are not specifically excluded from this study, there will be no specific efforts to target these populations.

8- Subject Accrual

Eligible subjects will be identified by physicians, nurse practitioners, and physician assistants at the Abramson Cancer Center and PPMC. A total of 200 patients will be included in this study.

9- Subject Recruitment & Screening

All adult patients being evaluated by the Penn Thoracic Oncology group meeting inclusion/exclusion criteria will be screened for admission into the study. All prospective research subjects will meet with a study team member, the study will be explained, questions answered and the Informed Consent Process will be initiated

10- Data

This study will collect the following specific personal health identifiers (PHI) and other data elements for use at Penn. These data elements will be stored electronically in REDCAP, and will only be accessible to Penn study members. See **section 12** for specific data elements

INVESTIGATIONAL AGENTS

11. Drugs/devices (if applicable)

N/A

STUDY PROCEDURES

12. Procedures

1. Informed consent
2. Collection of baseline clinical information (chart review)
 - a. Baseline demographic data (sex, race, ethnicity)
 - b. Tobacco history
 - c. Medical history
 - d. Performance status
 - e. Baseline tumor related variables, including histology, immunohistochemistry results, TNM stage, sites of tumor involvement
 - f. Results of staging CT scans
 - g. Mutation status as determined by clinical testing of tumor material
 - h. Treatment regimens, including chemotherapy regimen, doses
3. Blood will be drawn once at baseline prior (up to 50 ml), and the frequency of research blood collection will not exceed the lesser of 50 mL or 3 mL/kg in an 8 week period and will not occur more frequently than 8 times per year. When possible, research blood samples will be drawn at the same time as the clinical sample to minimize discomfort and inconvenience to the patient. The listed time points below are approximations and will depend upon when the patient is having blood drawn for clinical purposes
 1. Baseline – up to 30 ml
 2. 2-4 weeks - up to 20 ml
 3. 8-12 weeks – up to 30 ml
 4. 14-16 weeks – up to 20 ml
 5. 18-24 weeks – up to 30 ml
4. Subjects will be asked if they are willing to provide a single urine specimen in a sterile specimen cup at the time of enrollment
5. Although the vast majority of patients will have had tissue sequencing and immunohistochemical analysis to determine PD-L1 expression, if these analyses have not been performed, we may request that tumor tissue undergo this testing provided sufficient material is available. The result of this information may be disclosed to the patient and primary oncologist.
6. Longitudinal Data collection
 - a. CT imaging to monitor treatment response
 - b. Date of progression, and sites of progression.
 - c. Date of death, if prior to end of study period
7. Analysis of blood and tissue samples. Samples may undergo the following analyses:
 - a. Blood samples will undergo isolation of circulating free DNA and identification of specific mutations using either a PCR or sequencing approach
 - b. Identification of specific proteins or cell surface markers using various protein measurement methods (e.g. mass spectroscopy, flow cytometry)

STATISTICAL PLAN

13. Sample Size Determination

This is a pilot analysis to determine the role of novel biomarkers for use as predictive markers in patients with lung cancer receiving immunotherapy. We are unable to conduct formal sample size analysis given the pilot nature of this study.

14. Statistical Methods

We will use descriptive statistics for variables collected. We will describe the demographic characteristics of subjects using frequencies and percentages for categorical variables and medians and ranges for quantitative variables. Data analysis will focus on the following analyses (based on our primary objective)

1. Prognostic markers: The analysis will determine the association with response rate, PFS, and OS.
2. When feasible, we will calculate the correlation between markers identified in the blood and in the primary tumor.

SAFETY & ADVERSE EVENTS

15. Potential Risks

The risk of study participation is minimal. The two main risks are loss of confidentiality and the risk of venipuncture. A number of mechanisms are in place to protect subject confidentiality (see above). The risk of venipuncture is minimal. There may be bruising or bleeding, and rarely infection. The overall amount of blood drawn for this study is not to exceed 50 ml not to exceed in an 8 week period and will not occur more frequently than 8 times per year and should not have any clinical implications for study participants.

16. Potential Benefits

Discovery of a minimally invasive biomarker to predict response to immunotherapy has the potential to significantly alter the current management of patients with lung cancer. This study may lead to the development of new methods for the management of patients with lung cancer receiving immunotherapy.

17. Confidentiality & Data Storage

Precautions will be taken to ensure that strict confidentiality is maintained. All source documents will be identified by a unique study ID number (unique for this project). No results will be reported in a personally identifiable manner. Study data will be maintained either on a study-dedicated computer whose files are password protected or in a locked filing cabinet to which only the investigators and their designated staff have access. Data that will be disclosed outside of Penn:

- a. Baseline demographic data (sex, race, ethnicity)
- b. Tobacco history
- c. Performance status
- d. Baseline tumor related variables, including histology, immunohistochemistry results, TNM stage, sites of tumor involvement
- e. Results of staging CT scans
- f. Mutation status as determined by clinical testing of tumor material
- g. Treatment regimens, including chemotherapy regimen, doses

18. Data Safety & Monitoring

PROJECT TITLE: A PILOT STUDY TO DEVELOP PREDICTIVE BIOMARKERS FOR THE RESPONSE TO

IMMUNOTHERAPY IN LUNG CANCER

PRINCIPAL INVESTIGATOR/FACULTY SPONSOR: [name], MPH

PROTOCOL SUMMARY VERSION DATE: August, 2018 (VERSION 2)

Safety data will be monitored by the principal investigator formally on a quarterly basis in the course of study conduct. We plan to have our data reviewed manually by the study coordinator who will bring any discrepancies to the attention of the study team for investigation and resolution.

19. Risk/Benefit Ratio

Although there is no immediate, direct benefit to the individual participants of this study, there is considerable potential benefit to future subjects, including participants in this study, and to the community as a whole. Physicians may be able to better predict the patients most likely to benefit from receiving immunotherapy for the treatment of lung cancer. In view of the minimal risks to study participants and considerable benefits of the study, the risk/benefit ratio is extremely favorable.

REGULATORY & ETHICAL CONSIDERATIONS

21. Informed Consent

Informed consent will be obtained during the patient's in-patient or out-patient visit at UPHS. Only competent patients will be approached to participate. This will be judged by an informal assessment by the investigator, but a mini-mental status exam will be performed if necessary. The goals of the study will be described by a study coordinator. The consent document will be reviewed and provided to prospective subjects. Comprehension of the consent document will be assessed by the study coordinator and investigators.

STUDY FINANCES

22. Funding Source

None

23. Compensation to Subjects for Participation

No compensation will be provided for the participants.

24. Conflict of Interest

All University of Pennsylvania investigators will follow the University conflict of interest policy. There is no conflict of interest for the principal investigator or any member of the study staff.

PUBLICATION PLAN

25. Publication Plan

Results of the proposed research may be presented at intramural conference sessions within the Abramson Cancer Center, and in various oral, print and electronic publications. The principal investigator holds primary responsibility for presentation of the results of the study.

References

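### The primary outcome promises validation of response-predicting markers, but no planned analysis tests a marker in data not used to choose it

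*Combined protocol and SAP*

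**What the plan says.** Section 3 (Study Objectives) names a single primary outcome: "Discovery and validation of new blood based biomarkers that predict response to immunotherapy in NSCLC". The only secondary outcome is storing samples for later research.

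Other sections are more modest or less definite:

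- Section 1 (Abstract): "The goal of this study is to broadly discover and evaluate the utility of blood based biomarkers".
- Section 2 (Background): "these biomarkers will be assessed for their ability to predict responsiveness". It also lists correlation with radiographic response, "ability to detect lung cancer specific genetic changes present in the primary tumor", and impact on prognosis. It names no method or separate data for judging a marker once chosen.
- Section 5 (General Design): "Single center, longitudinal cohort study of NSCLC patients receiving immunotherapy with biomarker evaluation". The same section uses the phrase "Given the exploratory nature of this study" when explaining that hypotheses will change as results come in.
- Section 8 (Subject Accrual): "A total of 200 patients will be included in this study". The cohort is not divided into discovery and validation sets.
- Section 13: the pilot nature of the study is given as the reason for having no formal sample size calculation.

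Section 14 (Statistical Methods) ties itself to section 3: "Data analysis will focus on the following analyses (based on our primary objective". Beyond descriptive statistics it lists two items. The first is the association of prognostic markers with response rate, PFS and OS. The second, where feasible, is the correlation of blood markers with markers in the primary tumor.

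**The concern.** Discovering a marker and validating it are different claims. Discovery asks which of many candidates is associated with response in these patients. Validation asks whether the chosen candidate, with its direction and cut-point fixed, still predicts response in data that played no part in choosing it. Section 3 promises both; section 14 has analyses for the first only.

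The gap matters more here because the candidate set is open-ended (mutations in cell-free DNA, proteins and cell-surface markers by several methods; section 12, item 7) and the hypotheses are expected to evolve. Choosing the best-looking marker and reporting its accuracy in the same patients is therefore a foreseeable path, and accuracy obtained that way can be too favourable. A study that completed every listed analysis could then describe a marker as validated because its primary outcome uses that word.

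Research-only markers are not disclosed to treating physicians and drive no treatment decisions (section 5). The consequence falls on the study's conclusion and on later studies built on it.

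**Working it through.** **1. Is there a figure to reproduce?** No. The 200 patients are stated without derivation, and there is no alpha, power, effect size or accuracy measure. The main check is textual.

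**2. Each element that might count as validation.**

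| Element | Where | Tests prediction of response in data not used for selection? |
|---|---|---|
| Descriptive statistics | Section 14 | No |
| Association with response rate, PFS, OS | Section 14, item 1 | No; same cohort, no held-out or resampled step |
| Blood-tumor correlation | Section 14, item 2 | No; at most analytical agreement with tissue |
| Assessing ability to predict | Section 2 | States an intent; no method or data set |
| Stored samples | Sections 2 and 3 | Future use unspecified; validation neither planned nor excluded |

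Nothing in sections 12 to 14 adds a split, resampling, a locked marker or an external cohort. The conclusion rests on this table alone.

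**3. False positives in association testing (illustration).** With m independent null markers each tested at 0.05, the chance of at least one false positive is 1 − 0.95^m: 0.40 (m = 10), 0.64 (m = 20), 0.99 (m = 100).

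**4. Optimism in the selected marker (illustration).** The documents supply the 200 patients (section 8). The rest is assumed: 200 × 0.20 = 40 responders, borrowing the background figure, which is for durable response; 200 × 0.40 = 80 as an alternative; M = 10, 20 or 100 normal markers; pairwise correlation 0 or 0.8; all noise, or one real marker with the stated true AUC.

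AUC = (R1 − n1(n1 + 1)/2)/(n1·n0), where R1 is the rank sum of the n1 responders and n0 is the number of non-responders. The marker with the largest max(AUC, 1 − AUC) is selected. Inflation is its apparent AUC minus its true AUC (0.50 if a noise marker is picked). Means over 2000 replicates, simulation SE 0.0004 to 0.0014, shown for M = 10/20/100 (ranges over M in the last three cells):

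| Responders, correlation | All noise | True 0.60 | True 0.65 | True 0.70 | True 0.75 |
|---|---|---|---|---|---|
| 40, 0 | 0.097/0.110/0.139 | 0.064/0.085/0.121 | 0.029/0.043/0.078 | 0.004/0.010/0.025 | −0.001/0.001/0.003 |
| 40, 0.8 | 0.073/0.081/0.097 | 0.038/0.045/0.055 | 0.022/0.025/0.031 | 0.009/0.011/0.013 | 0.003/0.000/0.005 |
| 80, 0 | 0.078/0.091/0.114 | 0.039/0.052/0.088 | 0.009/0.015/0.034 | 0.000/0.000/0.006 | 0.000 |
| 80, 0.8 | 0.060/0.066/0.079 | 0.025/0.029/0.038 | 0.01 to 0.03 | at most 0.006 | about 0 |

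An extreme case, 1000 independent markers with 40 responders (200 replicates), gives 0.175 if all are noise and 0.076 with one real marker at 0.70.

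Part of the noise figure comes from choosing the direction, not the marker: one null marker with no competitor averages 0.540 with 40 responders, so about 0.04.

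**5. Does an honest step remove the optimism?** Repeated 5-fold cross-validation was run with selection inside each training fold (40 responders, independent markers). Entries are apparent AUC / true AUC of the selected marker / cross-validated AUC.

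| | M = 20 | M = 100 |
|---|---|---|
| All noise | 0.611/0.500/0.501 | 0.641/0.500/0.504 |
| True 0.60 | 0.628/0.545/0.539 | 0.647/0.521/0.520 |
| True 0.70 | 0.702/0.691/0.684 | 0.699/0.669/0.650 |
| True 0.75 | 0.747/0.749/0.744 | 0.751/0.747/0.741 |

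The cross-validated mean stays within 0.02 of the truth throughout. A held-out third likewise returns a mean of 0.50 for a selected noise marker.

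**The case against.** The strongest reply is that this is an omission in a self-declared pilot, not an error. Section 14 says where analysis will focus, which need not be exhaustive. Section 2 states an intent to assess prediction. Nothing forbids testing a marker in later-enrolled patients during the five-year study. Validation is undefined and could mean agreement of blood with tumor. Section 3 also describes the overall objective as building a sample-collection system, and the documents never say that a marker will be declared validated.

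Some of this stands. The pilot and exploratory framing warns the reader, the harm depends on how results are worded, and a wording change cures it. The illustration also measures something the plan does not specify: section 14 names no AUC, every other input is assumed, and the resulting range is wide.

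The rest does not supply the missing step. A non-exhaustive list adds no analysis, and an intent is not a method. Agreement with tumor does not test prediction of response, which is what the primary outcome specifies. The pilot label explains the absent sample size calculation; it does not explain the word validation. It points the other way, since the abstract's more modest goal already fits the analyses.

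**Conclusion.** The concern holds. The sole primary outcome claims a property, validation of predictive markers, that none of the planned analyses can deliver. As written, the plan supports discovery only. This follows from the text and needs no assumed number.

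The size of the risk cannot be derived from the documents. Under the assumptions above, mean AUC inflation runs from near zero for a strong real marker (true AUC 0.75) to 0.06 to 0.14 when 10 to 100 markers are all noise, and to 0.175 in the 1000-marker case. It is largest when true signals are weak or absent, which is the situation validation is meant to detect. PFS and OS were not illustrated.

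This should be fixed: it concerns the primary outcome and what the study may conclude, but not participants' care.

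**What to change.** **Section 3, one of two changes.** Either delete the words *and validation*, which is enough to remove the contradiction, or insert *internal* before *validation* and state that external validation needs another cohort.

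**Section 14, only if internal validation is kept.** Add, for example: *Performance of any marker, cut-point or model selected from these data will be estimated either by resampling that repeats all marker selection and cut-point choice within each resample (for example repeated cross-validation), or by testing a locked marker and cut-point in patients not used to select it, and reported with a confidence interval.* The performance measure for each outcome and the interval method should be named, because cross-validation folds are not independent. The choice of route is the sponsor's.

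**Cost.** Deleting the words costs nothing. Keeping internal validation needs one or two sentences and some analysis code, with no extra patients or assays. The price is less favourable and noisier accuracy:

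- The SD of the cross-validated AUC was about 0.05 to 0.07 with noise markers only and 0.04 to 0.09 with one real marker.
- Choosing in half the patients and testing in the other half was noisier (SD 0.06 to 0.13). It also found a real marker less often: 74% against 96% of data sets with 20 independent markers, true AUC 0.70 and 40 responders.
- A single 2:1 split would leave about 13 responders among 66 test patients at a 20% response rate. By the Hanley-McNeil formula, an AUC of 0.70 then has SE 0.088 and 95% half-width 1.96 × 0.088 = 0.17, against 1.96 × 0.050 = 0.10 with all 200.

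### Section 14 plans only an association between marker and outcome and names no measure of predictive accuracy, so a weakly discriminating marker could be reported as predicting response.

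*Combined protocol and SAP*

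**What the plan says.** The aim is framed as prediction throughout. The Abstract sets out to "evaluate the utility of blood based biomarkers for use in measuring and predicting response to immunotherapy". The Background says that what is needed is "a biomarker that could accurately predict the patients most likely to derive benefit from immunotherapy", and adds that the study's markers will be assessed for their ability to predict responsiveness. Section 3 gives the primary outcome as "Discovery and validation of new blood based biomarkers that predict response to immunotherapy in NSCLC".

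Section 14 says that its analyses follow from the primary objective and lists two:

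- Item 1, labelled as concerning prognostic markers: "The analysis will determine the association with response rate, PFS, and OS".
- Item 2, to be done when feasible: "we will calculate the correlation between markers identified in the blood and in the primary tumor".

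Before these come descriptive statistics for the variables collected and for demographics. Section 8 fixes the size: "A total of 200 patients will be included in this study". Section 13 gives no derivation of that number: "We are unable to conduct formal sample size analysis given the pilot nature of this study".

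No section names a test, a significance level, a marker cut-off, an accuracy measure, or a result that would count as predicting response.

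**The concern.** Whether a marker predicts response is a question about discrimination: how well it separates responders from non-responders, and how often it is wrong in individual patients. An odds ratio, hazard ratio or difference in group means does not answer this. It can be large and precisely estimated while the marker distributions of responders and non-responders overlap heavily. Item 2 does not help, because agreement between blood and tumour says nothing about outcome.

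This is separate from whether an independent validation sample exists. An association repeated in a fresh cohort would still leave the error rates unstated.

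At stake is what the study can claim. Section 16 expects a marker of this kind to change the management of lung cancer, and Section 25 foresees publication. A paper could follow Section 14 to the letter, describe a marker as predictive because it is associated with response, and give readers no means of judging how useful it is.

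**Working it through.** The plan states no accuracy, effect size or power figure, so there is nothing of its own to reproduce. The check asks how weak a marker can be and still show a clear association at this sample size.

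**Inputs**

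- N = 200 (Section 8).
- Response rate about 20%, the background figure for durable response in unselected patients (Abstract). This gives 40 responders and 160 non-responders. It is not a design assumption for this cohort, so 15% to 45% is also run.
- Marker positive in 50% of patients: assumed. 25% and 75% are also run.
- Two-sided 5% level: assumed, because the plan gives none.

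**1. Illustrative binary marker**

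| | Responder | Non-responder | Total |
|---|---|---|---|
| Marker positive | 30 | 70 | 100 |
| Marker negative | 10 | 90 | 100 |
| Total | 40 | 160 | 200 |

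Association:

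- Odds ratio = (30 × 90)/(70 × 10) = 2700/700 = 3.86.
- Chi-square = 200 × (30 × 90 − 70 × 10)² / (100 × 100 × 40 × 160) = 12.5, p = 0.0004 (Fisher exact p = 0.00065).

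Accuracy in the same table (Wilson 95% CI):

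- Sensitivity = 30/40 = 75% (60 to 86), so 10 of 40 responders are called negative.
- Specificity = 90/160 = 56% (49 to 64).
- PPV = 30/100 = 30% (22 to 40), so 70% of positives do not respond.
- NPV = 90/100 = 90% (83 to 94).
- AUC = (0.75 + 0.5625)/2 = 0.66.
- Misclassified = (70 + 10)/200 = 40%.

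**2. Varying marker positivity.** These are the weakest tables with Fisher p < 0.05 at 40 responders:

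| Marker positive | Responders v non-responders positive | p | Sensitivity | PPV | AUC | Misclassified |
|---|---|---|---|---|---|---|
| 25% | 16/40 v 34/160 | 0.023 | 40% | 32% | 0.59 | 29% |
| 50% | 27/40 v 73/160 | 0.021 | 67.5% | 27% | 0.61 | 43% |
| 75% | 35/40 v 115/160 | 0.043 | 87.5% | 23% | 0.58 | 60% |

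**3. Varying the response rate.** With the marker positive in 50%, the weakest significant tables give:

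- 15% response: AUC 0.62, PPV 21%.
- 30% response: AUC 0.58, PPV 37%.
- 45% response: AUC 0.58, PPV 53%.

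Discrimination stays weak across the range. The low PPV does not: it rises with the response rate.

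**4. Continuous marker.** With R responders and NR non-responders, the null standard error of the AUC is √[(N + 1)/(12 × R × NR)]. For R = 40 and NR = 160 this is √(201/76,800) = 0.0512. The smallest AUC with p < 0.05 is therefore 0.5 + 1.96 × 0.0512 = 0.60. The corresponding values are 0.61 at 15% response (30 v 170) and 0.58 at 45% (90 v 110).

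**5. Precision of accuracy estimates.** With 40 responders, the 95% half-width for sensitivity is 1.96 × √(0.8 × 0.2/40) = 12.4 points at 80%, and 1.96 × √(0.5 × 0.5/40) = 15.5 points at 50% (normal approximation).

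**The case against.** The best defence is that *association* is an open word. For a binary marker, the natural output is the response rate by marker status. In the illustration that is 30% against 10%, which are the PPV and 1 minus the NPV. So a report that follows Section 14 could contain the predictive values, and the plan does not rule out an AUC. This stands as far as it goes: the fault is that accuracy is not specified, not that it is excluded. But nothing commits the study to reporting accuracy, and for a continuous marker an odds or hazard ratio does not supply it.

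It is also fair to say that the study is an exploratory pilot, that the overall objective is a system for collecting samples, and that association is an ordinary analysis for prognosis, which the Background lists among its aims. Under Section 5, research-stage results are not disclosed and guide no treatment decisions, and the data will remain available for later analysis. These points limit the consequence. They do not remove the mismatch with the primary outcome. Section 13 uses the pilot status to excuse the absent sample size calculation, but accuracy estimates with confidence intervals are descriptive and need no such calculation.

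Two stronger readings are tempting, and the documents do not support either:

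- A reader might infer that the plan declares markers predictive on a small p-value. It names no test, p-value or level. It sets no criterion at all, and the p-values above are only a yardstick.
- A reader might infer that a significant marker could typically misclassify most patients. The illustration misclassifies 40%. At 20% response, exceeding half at p < 0.05 needs a marker positive in at least 121 of 200 patients, about 60%. At 45% response, the worst significant table reaches only 52%.

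**Conclusion.** The concern holds in this form: the primary outcome is prediction of response, the only planned analysis of marker against outcome is an unspecified association, and no measure of predictive accuracy appears anywhere in the plan. At the planned size, an odds ratio of 3.9 with p = 0.0004 can go with an AUC of 0.66, and nominal significance can be reached at an AUC of about 0.60 (0.58 to 0.61 for response rates of 45% to 15%).

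These figures rest on the background 20% response rate, an assumed 50% marker positivity and an assumed two-sided 5% level. The weak discrimination is stable over the ranges tried. The statement that most marker-positive patients do not respond depends on a low response rate and fails at 45%. The plan should be changed, but the flaw does not undermine the sample collection or the data.

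**What to change.** Amend Section 14 item 1 as follows:

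- For each marker at the baseline draw, report the AUC for response with a 95% CI, and a C-index for PFS and OS, alongside the association.
- Report sensitivity, specificity, PPV and NPV with 95% CIs at a cut-off fixed before the outcome data are examined. The protocol contains no cut-off at present. If one is derived from these data, correct the accuracy estimates for optimism by cross-validation or bootstrap, because a cut-off tuned on the same patients will flatter the marker.
- State that any claim that a marker predicts response rests on these measures and not on an association alone.

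The cost is a few lines of text and a little more analysis. Section 12 already provides the baseline blood, CT response, and progression and death dates. The downside is wide intervals, about 12 to 15 points either side for sensitivity with 40 responders, and some markers will look less impressive than their associations suggest.
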